# 6. **RESEARCH METHODS**

#### 6.1 Study Design

This is an observational, multicountry, retrospective, post-authorization safety study (PASS) based on the secondary data collected from medical records of transplant recipients treated with maribavir who are refractory to prior anti-CMV treatment and are diagnosed with ESRD or severe chronic renal disease requiring peritoneal dialysis or hemodialysis.

The study does not interfere with standard medical care and will not impact the current treatment of the study participants.

Physicians will be asked to screen existing medical records and consecutively include eligible patients until the study meets the expected sample size. Chart reviews will be performed regardless of the patients' survival status at the time of initiation of data abstraction.

The study design will include a study follow-up period covering the full duration of the treatment course with maribavir from index date (Day 0: the day of initiation of the first maribavir treatment course during the eligibility period) until death, end of data availability, end of treatment or treatment discontinuation +7 days post-treatment, whichever occurs earliest. An additional 7-day grace period following treatment discontinuation or end of treatment is allowed to capture potentially relevant events that may occur in the immediate period after the censoring event.

Eligibility period is defined as the period of time within which the index date must fall for the patient to be included in the study. Index date should have occurred between the commercial launch date of maribavir and 3 months before the first data abstraction. These dates will be different for each country. Data collection will span 2 main periods of time anchored to the date of index event:

[figure not shown]
- Pre-index event period: begins on the date of diagnosis of kidney disease or underlying health issue that leads to the transplant and ends 1 day before the index date during the eligibility period
- Post index event period: begins on 1 day after the index date during the eligibility period and ends at the earliest of death, completion of maribavir treatment+7 days post-treatment completion, maribavir discontinuation for any reason+7 days post-treatment, or end of data availability

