#### 02 June 2023

- Current CMV infection
  - Date of onset of infection/diagnosis
  - Refractory characteristics
    - Antiviral agent to which CMV infection is refractory
    - Type of drug-resistant mutations (if applicable)
  - Agent that patient is refractory to
  - o Classification of CMV infection
    - Asymptomatic
    - Tissue-invasive CMV disease
    - CMV syndrome
  - Prior anti-CMV medication used to treat the current CMV infection
    - Induction and maintenance therapy received for transplant, rejection treatment, and other adjuvant/related therapy
    - Start/end dates
    - Other anti-CMV prophylaxis and treatment
    - Other anti-infective agents
  - AEs including renal toxicity from prior anti-CMV treatment
- Current transplant status
  - Date of transplant
  - Type of transplant
    - HSCT
      - Autologous
      - Allogeneic
    - SOT
      - Heart transplant
      - Lung transplant
      - Liver transplant
      - Pancreas transplant
      - Intestine transplant
      - Kidney transplant
      - Other transplant
  - Reason for transplant
    - Leukemia (acute myeloid)
    - Leukemia (chronic myeloid)
    - Leukemia (acute lymphocytic)
    - Lymphoma (non-Hodgkin's)
    - Myelodysplastic syndrome
    - Other myeloid malignancy
    - Other
  - Stem cell source (for HSCT)
    - Bone marrow
    - Peripheral blood stem cell
    - Cord blood
    - Other

02 June 2023

- o CMV serostatus
  - Donor positive/recipient positive
  - Donor negative/recipient positive
  - Donor positive/recipient negative
  - Donor negative/recipient negative
- Current GVHD status (for HSCT patients only)
  - Acute GVHD status
    - Presence
    - Absence
    - Grade
  - Chronic GVHD status
    - Presence
    - Absence
    - Grade
- Relevant comorbidities ongoing or diagnosed at index date and treatment

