# 6.5 Study Size

The source population for the current PASS comprises of post-transplant patients with CMV infection/disease refractory (with or without resistance) to prior antiviral treatments and a post-transplant diagnosis of comorbid ESRD or comorbid severe chronic renal disease requiring peritoneal dialysis or hemodialysis. As such, study size will be dependent on the patterns of use of maribavir in routine clinical practice during the first years after launch for an indication that is expected to be ultra rare.

Considering the eligibility criteria, coupled with the rarity of the source population, the target sample size for this PASS is approximately 10 patients. This target sample size was determined by practical and feasibility assessments, and findings from the pivotal SHP620-303 (SOLSTICE) trial. Of the 352 randomized patients in the SOLSTICE trial, only 11 patients with 8 (2.3%) on maribavir treatment had severe chronic renal disease, defined as creatinine clearance <30 mL/minute according to the Cockcroft-Gault formula (Avery et al. 2022; Sampson and Drury 1992). Notably, patients in the SOLSTICE trial were not on dialysis; the current study aims to further select patients from an already rare population. Although no formal hypotheses have been prespecified and sample size calculations are not applicable, best estimates and 95% confidence intervals (CIs) for various sample sizes are presented in Table 3.

	Sample Size		
% of Participants with AEs	10	20	
5%	38.1% (0%, 38.1%)	24.7% (0.1%, 24.9%)	
20%	53.1% (2.5%, 55.6%)	37.9% (5.7%, 43.7%)	
35%	60.4% (9.3%, 69.6%)	43.8% (15.4%, 59.2%)	
50%	62.6% (18.7%, 81.3%)	45.6% (27.2%, 72.8%)	
65%	60.4% (30.4%, 90.7%)	43.8% (40.8%, 84.6%)	
80%	53.1% (44.4%, 97.5%)	37.9% (56.3%, 94.3%)	
95%	38.1% (61.9%, 100%)	24.7% (75.1%, 99.9%)	

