# 6.7.1 Statistical Methods

Unless otherwise specified, all statistical analyses will be descriptive in nature. Continuous variables will be described by the number of eligible participants and missing data, mean, standard deviation, median, first quartile, third quartile, and minimum and maximum values. Categorical variables will be described as the total number of participants and relative percentage per category. Percentages will be calculated using the most appropriate denominator. Two-sided 95% CIs will be reported as appropriate.

Should missing data occur, missing data will not be imputed and the data will be analyzed as they are recorded in the study eCRFs. However, for all missing dates, some date imputation may be performed. The general imputation rules will be described in the SAP. Missing data may be included as a separate category in some cases, depending on the nature of the variable. Unless otherwise specified in a table's footnote, missing values will not be included in the denominator for summarizing a categorical variable's distribution. If the eCRF includes a selection of "unknown," these responses will not be considered missing responses and will be included in the distributions.

Descriptive analysis will be performed on the variables listed in Section 6.4. Year of birth will be analyzed as age and age group, and dates would be as duration or index days/weeks. Detailed definitions of additional variables that may be derived from the collected data for the statistical analysis will be included in a separate SAP.

Incidence of each outcome will be expressed per person-year of exposure to account for varying length of follow-up. Incidence rates will be calculated as the number of patients with an event of interest, divided by the number of person-years at risk, ie, the summed person-year of maribavir exposure. Only new cases will be included in the numerator; patients with existing AEs at the index date who reported the AE before the index date will not be counted, and patients who initially experience AEs at index or at the post index date will be counted only once in the numerator (ie, worsening outcomes will not be counted as new cases). The following definitions will be used to estimate incidence rates:

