- Person-days at risk for an individual will be defined as the total number of days of maribavir exposure (ending at the date of the outcome of interest, the final dose of maribavir +7 days, death, or end of data availability). For each incidence rate, 95% CIs will be calculated using exact methods.
- The follow-up period (person-days) will be defined as the period from the index date until the earliest of: 7 days following the date of discontinuation of initiated maribavir medication, end of data availability, or death.
- Person-years will be calculated by dividing person-days by 365.

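### Section 6.7.1 gives conflicting denominators for the first-event incidence rate, and excludes patients with pre-existing events from the numerator only

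*Protocol*

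**What the plan says.** All of the following comes from Protocol Section 6.7.1 unless another section is named.

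- **Main text.** The rate is the number of patients with the event "divided by the number of person-years at risk, ie, the summed person-year of maribavir exposure". Nothing here stops time at the event or adds 7 days.
- **First bullet.** Person-days at risk are counted in exposure days, with the clock "ending at the date of the outcome of interest, the final dose of maribavir +7 days, death, or end of data availability".
- **Second bullet.** "The follow-up period (person-days) will be defined as the period from the index date until the earliest of" discontinuation +7 days, end of data availability or death. The outcome is not among the stopping points.
- **Third bullet.** "Person-years will be calculated by dividing person-days by 365". It does not say which person-days.
- **Numerator.** Each patient counts once, and "patients with existing AEs at the index date who reported the AE before the index date will not be counted". No matching rule is given for person-time.

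Section 6.7.1.1 asks for both a first-event rate and a total-event rate. It places the first-event rate over the follow-up period, and bases the analyses on everyone who received at least one dose. Section 6.7.1.2 asks for the same two rates for each adverse event of special interest (AESI).

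On the start of counting, Section 6.1 says that the post-index period "begins on 1 day after the index date during the eligibility period". Section 6.4.2 collects safety data during the index and post-index period, and Section 6.7.1 counts events at index.

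**The concern.** A first-event rate needs time during which a first event can still occur. Time after a patient's first event does not qualify. Nor does the time of a patient who already had the event and so cannot enter the numerator. Two programmers working from Section 6.7.1 could choose different denominators, each pointing to the text, and report different values for the primary endpoint. The errors at issue (not stopping at the event, keeping prevalent time) both lower the rate. That is the unhelpful direction in a safety study meant to fill a gap in the risk management plan.

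The prevalence question is not remote. Several AESIs, such as diarrhoea, nausea and tissue-invasive CMV disease, can plausibly be present when maribavir starts, and Section 6.4.4 records the CMV classification at index.

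**Working it through.** **The plan's own figure.** The only precision figures are in Table 3 (Section 6.5). They reproduce as Clopper-Pearson intervals; for example, 5 of 10 gives 18.7% to 81.3%, width 62.6 points. They concern proportions and do not bear on person-time. The protocol states no rate, person-time, onset time or prevalent share, so the inputs below are assumptions.

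**Inputs.**
- 10 patients: "the target sample size for this PASS is approximately 10 patients" (Section 6.5).
- 63 days per patient: 8 weeks of treatment in the Phase 3 trials (Section 4) is 56 days, plus 7. This is a proxy, since the protocol fixes no treatment length for this cohort.
- Risk r of a first event over the 63 days: 5% to 95%, the range of Table 3.
- Share f of patients with the event before index: varied.
- Constant hazard, so expected time to first event or end of follow-up is 63 × r / (−ln(1−r)) days per patient at risk.

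**Step 1: time not stopped at the event, no prevalent patients.** The understatement factor is 63 divided by that expected time, which is −ln(1−r) / r.

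| r | Factor |
|---|---|
| 5% | 0.0513/0.05 = 1.03 |
| 20% | 0.2231/0.20 = 1.12 |
| 50% | 0.6931/0.50 = 1.39 |
| 80% | 1.6094/0.80 = 2.01 |
| 95% | 2.9957/0.95 = 3.15 |

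If first events cluster early, the factor is larger. Take 9 of 10 patients with a first AE on one day and the tenth followed for 63 days:
- Day 10: 9×10 + 63 = 153 days, so 9/(153/365) = 21.5 per person-year. Unstopped, 9/(630/365) = 5.2. Ratio 630/153 = 4.1.
- Day 7: 9×7 + 63 = 126 days, so 26.1 per person-year against 5.2. Ratio 630/126 = 5.0.

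**Step 2: time stopped at the event, prevalent time kept.** The factor is 1 + [f/(1−f)] × [−ln(1−r)/r]. For r from 5% to 50%:
- f = 10%: 1.11 to 1.15
- f = 30%: 1.44 to 1.59
- f = 50%: 2.03 to 2.39

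**Step 3: one worked case on all readings.** Ten patients, 4 with the event before index, 3 of the other 6 with a first event on day 14. Exact Poisson 95% intervals are in brackets.

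| Denominator | Days | Rate per person-year | Shortfall |
|---|---|---|---|
| Stopped at event, prevalent removed | 3×14 + 3×63 = 231 | 4.74 (0.98 to 13.85) | reference |
| First bullet, prevalent kept | 231 + 4×63 = 483 | 2.27 (0.47 to 6.63) | 2.1-fold |
| Main text, 56 dosing days, all patients | 560 | 1.96 (0.40 to 5.71) | 2.4-fold |
| Second bullet, all patients | 630 | 1.74 (0.36 to 5.08) | 2.7-fold |

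**Step 4: direction.** The exposure-only reading also drops the 7 post-treatment days, which shrinks the denominator (63/56 = 1.125). For a rare event this can outweigh the missing stop. One event on day 30 in 10 patients gives 30 + 9×63 = 597 days at risk against 560 exposure days, a rate 597/560 = 1.066 times the at-risk rate, or 6.6% too high.

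**The case against.** The strongest defence is that the text nearly resolves itself. The bullets are introduced as the operative definitions, the first does stop at the outcome, and the second fits the total-event rate. On that reading the exposure clause in the main text is a loose gloss, and the loss from not stopping at the event disappears. The reading is reasonable but not written down. It contradicts the main-text clause, Section 6.7.1.1 ties the first-event rate to the follow-up period that the second bullet defines, and the conversion bullet does not decide between them.

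It is also fair that no sentence says prevalent patients' time is kept. That is inferred from a rule stated for the numerator only, together with an analysis population of all dosed patients. Section 6.7 leaves derivations and censoring to the SAP, which may settle it. But the protocol has already fixed one half of the ratio, and followed as written that half gives a mismatch.

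Three stronger readings are tempting and are not supported:
- **A fixed two- to five-fold understatement.** No figure in the protocol yields it. For uncommon events with few prevalent patients the factor is about 1.0 to 1.5.
- **Every rate biased toward zero.** The total-event rate properly uses unstopped follow-up, and Step 4 shows a first-event rate that rises.
- **A GVHD rate diluted by solid organ recipients.** The entry "Current GVHD status (for HSCT patients only" in Section 6.4.4 governs recording at baseline. It does not define who is at risk for the outcome, and the number of HSCT patients is unknown.

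Finally, the study is descriptive, with about 10 patients. Counts, percentages, listings and narratives do not depend on this denominator.

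**Conclusion.** The point holds as an internal contradiction in how the primary rate is defined, with a one-sided exclusion of prevalent patients. It is more than detail left to the SAP, because following the main-text clause or the second bullet, or applying the numerator exclusion alone, gives a wrong first-event rate.

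The size depends on inputs the protocol does not supply. Under the 63-day, constant-hazard assumptions, the loss from not stopping at the event is negligible for rare events, about two-fold at 80% risk and about three-fold at 95%. It reaches four- to five-fold only if nearly all patients have a first AE within the first 7 to 10 days. Retained prevalent time matters little at 10% prevalence and roughly halves the rate at 50%. The intervals in Step 3 are wide and overlap, so the concern is a systematic shift and an ambiguous definition, not a conclusion that would necessarily reverse.

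The Day 0 versus Day 1 discrepancy is minor: one day in 63, or 1.6% of the time, and Sections 6.4.2 and 6.7.1 already point to the index date.

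**What to change.** In Section 6.7.1, give each rate its own denominator:

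- **First-event rate:** patients with a first event, divided by days from the index date to the earliest of first event, last dose +7 days, death or end of data. Exclude patients who had that event before index from both numerator and denominator.
- **Total-event rate:** all events, divided by unstopped follow-up from the index date to the earliest of last dose +7 days, death or end of data.

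Delete the clause equating person-years at risk with summed exposure where it applies to the first-event rate, and state in the conversion bullet which person-days are converted for each rate. Carry the same wording into the SAP and table shells.

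As a clean-up, align the start of the post-index window in Section 6.1 (and in the Abstract, which repeats it) with Sections 6.4.2 and 6.7.1, so that events and time both count from the index date.

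The cost is a few sentences and routine programming. The dates needed are already among the variables in Section 6.4, so no new data are required.

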#### Secondary objective:

To assess the occurrence of AESIs:

- Immunosuppressant drug concentration level increased
- Tissue-invasive CMV disease
- Relapse or progression of the underlying disease for which the transplant was performed
- Taste disturbance (dysgeusia)
- Nausea
- Vomiting
- Diarrhea
- Invasive fungal or bacterial infections
- GVHD

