Data from the patient's medical records will be abstracted by study investigators routinely involved in the care and treatment of the target indication (or delegates at the study site). Pseudoanonymous patient-level data will be transcribed, onto electronic case report forms (CRFs) to capture (i) baseline characteristics during the pre-index event period (eg, demographics, comorbidities, disease characteristics, treatment history) and (ii) follow-up data during the post index event period (eg, treatment patterns and safety events).

The primary endpoint is the incidence of any AE. The secondary endpoint is the incidence of the AESIs. The primary and secondary endpoints will be collected as part of the safety events in the post index event period. More details on the study endpoints are provided in Section 6.7.

Before study commencement, the protocol and relevant study documents approval will be obtained from an institutional review board (IRB) or ethics committee (EC). Participants must provide written informed consent before their inclusion in the study, as applicable. IRB/EC approval of a waiver of informed consent will be sought to allow record reviews of deceased patients.

A study design schematic is presented in Figure 1.

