#### 8. MANAGEMENT AND REPORTING OF ADVERSE EVENTS

#### 8.1 **Definitions**

#### 8.1.1 Adverse Events

An AE is any untoward medical occurrence in a subject administered a medicinal product and which does not necessarily have to have a causal relationship with this treatment. An AE can therefore be any unfavorable and unintended sign (including an abnormal laboratory finding), symptom, new disease or worsening in severity or frequency of a concomitant disease, temporally associated with the use of a medicinal product, whether or not the event is considered causally related to the use of the product.

Although abnormal laboratory values are typically not considered AEs, the following considerations may result in an abnormal laboratory value being considered an AE:

- A laboratory test result that meets the criteria for a serious AE
- A laboratory test result that requires the subject/patient to receive specific corrective therapy
- A laboratory abnormality that leads to discontinuation of therapy
- A laboratory abnormality that the healthcare provider considers to be clinically significant

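### The first-event incidence rate cannot count on-treatment worsening of a condition already reported at index, although the protocol defines such worsening as an adverse event

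*Protocol*

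**What the plan says.** Protocol Section 6.1 sets the primary endpoint: "The primary endpoint is the incidence of any AE". The secondary endpoint is the incidence of the AESIs. Sections 6.7.1.1 and 6.7.1.2 make the rate of first events per person-year at risk the first measure listed for each.

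Section 6.7.1 fixes how that rate is counted:

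- The general rule is: "Only new cases will be included in the numerator".
- A clause on events that predate treatment follows: "patients with existing AEs at the index date who reported the AE before the index date will not be counted".
- Patients whose first event falls at or after index are counted once. A parenthesis adds that "worsening outcomes will not be counted as new cases".
- Person-days at risk are all days of maribavir exposure, ending at the outcome, the last dose plus 7 days, death or the end of data. Section 6.7.1.1 bases the analysis on everyone who received at least one dose. Nothing removes the time of patients whom the numerator excludes.

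Section 8.1.1 defines an adverse event to include "new disease or worsening in severity or frequency of a concomitant disease, temporally associated with the use of a medicinal product". One AESI in Section 5 is "Relapse or progression of the underlying disease for which the transplant was performed".

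Section 6.4.4 collects, at index, acute and chronic GVHD presence and grade, whether CMV is tissue-invasive, and adverse events (including renal toxicity) from earlier anti-CMV treatment.

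**The concern.** The definition in Section 8.1.1 and the counting rule in Section 6.7.1 disagree about the same event. Worsening of an existing condition on treatment is an adverse event under the first. Under the second it cannot enter the rate if the condition existed at index and had been reported before it.

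The protocol expects such conditions: its index variables include the presence of GVHD and of tissue-invasive CMV disease, and both are AESIs. Diarrhea and nausea can also be present at index.

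The study is meant to fill a missing-information item in the EU risk management plan for a heavily comorbid population, where deterioration on treatment is one of the main harms to look for. Leaving it out of the lead measure makes the drug look safer. Because Section 6.7.1 states the rule outright, an SAP that counted worsening would contradict the protocol.

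**Working it through.** **The plan's own figure.** The protocol's only computed precision figures are in Table 3 (Section 6.5). For 2 of 10 patients the exact (Clopper-Pearson) 95% interval is 2.5% to 55.6%, width 53.1 points, as stated. All 14 cells reproduce to 0.1 point. Table 3 concerns proportions and is not affected by this point.

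**Which patients the rule drops**

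| Situation | AE under Section 8.1.1? | In the first-event numerator under Section 6.7.1? |
|---|---|---|
| First onset at or after index | Yes | Yes, once |
| Present at index, reported earlier, unchanged | Not as a worsening | No |
| Present at index, reported earlier, worsens on treatment | Yes | No |
| Resolved before index, recurs | Yes | Not clearly excluded |
| First progression of the transplant indication after index | Yes | Ambiguous |

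The third row is the conflict.

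**Size, for one AESI.** Inputs:

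- 10 patients (target in Section 6.5).
- Follow-up per patient is an assumption based on treatment durations in Section 4: 8 weeks + 7 days = 63 days, or 24 weeks + 7 days = 175 days.
- Event counts are assumptions: 1 new onset, and w = 0 to 3 patients whose reported condition worsens.

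Person-years: T = 10 × 63/365 = 1.73, or 10 × 175/365 = 4.79.

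Rate = x/T. Exact Poisson 95% limits: χ²(0.025; 2x)/(2T) and χ²(0.975; 2x+2)/(2T). The rule as written gives x = 1. Counting worsening gives x = 1 + w. A true new-onset rate would use x = 1 with person-time (10 − w) × days/365.

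At 63 days, per person-year:

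| w | Rule as written | Worsening counted | New onset only, excluded patients' time removed |
|---|---|---|---|
| 0 | 0.58 (0.01 to 3.23) | 0.58 | 0.58 |
| 1 | 0.58 (0.01 to 3.23) | 1.16 (0.14 to 4.19) | 0.64 |
| 2 | 0.58 (0.01 to 3.23) | 1.74 (0.36 to 5.08) | 0.72 |
| 3 | 0.58 (0.01 to 3.23) | 2.32 (0.63 to 5.93) | 0.83 |

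At 175 days the rule gives 0.21 (0.01 to 1.16) throughout, against 0.42, 0.63 or 0.83 with worsening counted.

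The ratio is 1 + w, that is 2 to 4, at either duration. It falls when there are more new onsets: with 2 new and 2 worsening at 63 days, 1.16 against 2.32, a factor of 2.

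These figures ignore the ending of person-time at the event. Allowing for it would shorten the denominator further when worsening is counted, so for given counts the ratio is a lower bound.

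The last column shows a separate fault. Even as a strictly new-onset rate the rule is too low, because patients who cannot contribute an event still contribute time: with w = 2, 1/1.73 = 0.58 against 1/1.38 = 0.72.

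**The case against.** Restricting an incidence rate to new cases and counting each patient once are conventional. The parenthesis about worsening is attached to the count-once clause for events first seen at or after index, so on its own it is ordinary. Both points stand. The conflict rests on the new-cases sentence and the clause on events already reported at index, and the convention also requires a denominator of patients at risk, which the protocol does not provide.

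Several stronger readings are tempting but not supported:

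- *That progression of the underlying disease can never be counted.* The AESI covers relapse or progression. A relapse after index is a new event. The underlying disease is the transplant indication, not necessarily an adverse event reported earlier, so a first progression after index can be read as new. The text is ambiguous and progression may be dropped, but a zero rate is not built in.
- *That CMV becoming tissue-invasive on treatment is lost.* A patient without tissue-invasive disease at index who develops it is a new case of that AESI.
- *That anything present before index is excluded.* The clause requires the event to exist at index and to have been reported earlier.
- *That every safety summary is biased.* Sections 6.7.1.1 and 6.7.1.2 also call for numbers and percentages of patients, total events, total-event rates, listings and narratives. The rule is not written for those, and with about 10 patients the listings and narratives carry much of the information.
- *That any earlier adverse event bars a patient from the any-AE rate.* Section 6.7.1 speaks of each outcome and an event of interest, which points to exclusion by term. It does not say so clearly, and that is a matter for clarification.

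The protocol leaves further derivations to an SAP that is not shown. That does not settle the point, because the counting rule is already fixed in the protocol.

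**Conclusion.** The concern holds for the first-event incidence rates of the primary and AESI endpoints. Followed as written, Section 6.7.1 leaves out on-treatment worsening that Section 8.1.1 calls an adverse event, keeps the person-time of the patients it leaves out, and so can only lower the rate. Under the assumed counts the understatement for a single AESI is two- to four-fold. The documents give no basis for predicting how many patients will worsen. The intervals are very wide either way, so the firm conclusion is the direction of the error.

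If exclusion is by term, the any-AE rate is affected only through patients with no other new event. If it is not, the effect could be much larger. Progression of the underlying disease is ambiguous. Because worsening can still appear in the other summaries, this should be fixed but does not invalidate the study. The report could otherwise show worsening in one table and omit it from the lead rate.

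**What to change.** Reword the counting paragraph in Section 6.7.1:

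- Count an event if it starts on or after index, or if it was present before index and worsens in severity, seriousness or frequency on or after index within the follow-up window. Date its onset at the worsening.
- Keep counting each patient once per term.
- Apply the already-present exclusion only to unchanged conditions and term by term, never to the any-AE rate.
- State that relapse or progression is judged relative to status at index.
- For any term from which a patient is excluded, remove that patient's person-time from the denominator.
- Optionally show strictly new-onset events as a separate row.

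The cost is one paragraph, one eCRF prompt to mark an event as new or as worsening of an existing condition (Section 6.4.2 lists no such variable), and slightly higher reported rates. It is best settled before abstraction starts, because worsening has to be captured from the charts.
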